3.4. Baseline and Other Variables

Baseline variables include the following data as part of the baseline characteristics:

- Demographics
- Medical history
- Physical examination

Other variables to be summarized include:

- E-diary completion
- Prior/concomitant vaccines

3.4.1. Demographics, Medical History and Physical Examination

The demographic variables are age at Dose 1 (in days), sex, race, and ethnicity. Age at Dose 1 vaccination in days will be derived as (Dose 1 vaccination date – date of birth + 1).

For subjects assigned to receive vaccine, but who are not vaccinated, the enrollment date will be used in place of the date of first vaccination.

Medical history will be categorized according to the Medical Dictionary for Regulatory Activities (MedDRA).

A physical examination will be performed. It will evaluate any clinically significant abnormalities within the following body systems: general appearance; skin; head, eyes, ears, nose, and throat; heart; lungs; abdomen; musculoskeletal; extremities; neurological; and lymph nodes. Clinically significant abnormal results will be recorded in the CRF.

3.4.3. Prior/Concomitant Vaccines and Concomitant Medications

The subject may receive vaccines with inactivated poliovirus, hepatitis B, or *Haemophilus influenzae* type b (either separately or in combination with diphtheria, tetanus, and pertussis antigens) at 2, 4, and 6 months of age. Measles, mumps, and rubella (MMR) vaccine may be administered at 12 months of age. Rotavirus vaccine may be administered orally at any time. Vaccines licensed and recommended for this age group other than the combination diphtheria, tetanus, and pertussis combination vaccine may be administered as specified in the protocol.

Concomitant medications will be recorded only if they were used to treat SAEs and NDCMCs. Concomitant and prior vaccines, and concomitant medications will be coded using the World Health Organization (WHO) Drug Dictionary (WHODD).

3.5. Safety Endpoints

Local reactions, systemic events, antipyretic/pain medication, AEs, SAEs and NDCMCs have been described above in the primary endpoints.

4. ANALYSIS SETS

Data for all subjects will be assessed to determine if subjects meet the criteria for inclusion in each analysis population prior to each analysis planned for this study (see Section 7). Classifications will be documented per standard operating procedures.

4.1. Safety Analysis Population

The **overall safety population** will include all subjects who receive at least 1 dose of c7vPnC (in Groups 1 and 2) or Prevnar 13 (in Group 3) and have safety data reported in the study. Subjects will be reported according to the vaccine actually received. The safety population will be the analysis population for safety and reactogenicity endpoints.

Additional safety populations will be defined as follows:

Dose 1 to Dose 3 Safety Population - Subjects receiving Dose 1 and having safety data between Dose 1 and the visit 1 month after Dose 3.

Dose 4 Safety Population - Subjects receiving Dose 4 and having safety data between Dose 4 and 1 month after Dose 4 for Groups 1 and 2 and having safety data between Dose 4 and Supplemental Dose for Group 3.

Supplemental Dose Safety Population - Subjects receiving Supplemental Dose and having safety data between Supplemental Dose and 1 month after Supplemental Dose.

If a subject's actual vaccine dose deviates from the planned vaccination within a particular safety population (eg, overall or Dose 1 to Dose 3), the subject data will be either analyzed for any by-dose presentation, or data will be presented in listings as appropriate according to the vaccine dose actually received.

4.2. Evaluable Immunogenicity Populations

The evaluable immunogenicity population will be defined for Dose 3 and Dose 4 separately.

The **Dose 3 evaluable immunogenicity population** will include any subject:

- 1. Who was eligible for the study.
- 2. Who was randomly assigned to receive the vaccine.
- 3. Who was 42 to 98 days of age, inclusive, on the day of Dose 1 for Groups 1 and 3 or who was 63 to 133 days of age, inclusive on the day of Dose 1 for Group 2.
- 4. Who received the vaccine to which he or she was randomly assigned, through Dose 3.
- 5. Who had a valid and determinate IgG concentration for at least 1 serotype from 1 month after Dose 3.
- 6. Whose blood collection was within 27 to 56 days, inclusive, after Dose 3.
- 7. Who had no other major protocol deviations as determined by the clinician or medical monitor.

The Dose 3 evaluable immunogenicity population will be the primary analysis population for immunogenicity results from the blood collected at 1 month after Dose 3.

The **Dose 4 evaluable immunogenicity population** will include any subject:

- 1. Who was eligible for the study.
- 2. Who was randomly assigned to receive the vaccine.

- 3. Who was 42 to 98 days of age, inclusive, on the day of Dose 1 for Groups 1 and 3 or who was 63 to 133 days of age, inclusive on the day of Dose 1 for Group 2.
- 4. Who received the assigned vaccine, as randomized, within the defined window for Dose 4 (365-386 days of age for Groups 1 and 3 and 386-421 days of age for Group 2; see Protocol Schedule of Activities).
- 5. Who received the vaccine to which he or she was randomly assigned at all 4 doses.
- 6. Who had a valid and determinate IgG concentration for at least 1 serotype 1 month after Dose 4
- 7. Whose blood collection was within 27 to 56 days, inclusive, after Dose 4.
- 8. Who had no other major protocol deviations as determined by the clinician or medical monitor.

The Dose 4 evaluable immunogenicity population will be the primary analysis population for immunogenicity results before and after Dose 4.

The blood collection window has been expanded by 1 extra day before, and 14 days after (see #6 above located under the Dose 3 evaluable immunogenicity population definition and #7 above for the Dose 4 evaluable immunogenicity population definition) the protocol-specified blood collection window of 28 to 42 days defined in the protocol, for consistency with established rules in the Prevnar 13 development program.

Subjects will be summarized according to their randomized vaccine in the immunogenicity analysis based on evaluable immunogenicity populations.

5. GENERAL METHODOLOGY AND CONVENTIONS

5.1. Hypotheses

No hypothesis testing will be performed, and also no formal statistical decision rules apply in this study. A descriptive estimation approach will be used to assess all safety and immunogenicity objectives. Nominal 95% confidence intervals will be calculated for all proposed endpoints.

5.2. General Methods

Time points for local reactions and systemic events refer to data within 7 days of each dose.

5.2.1. Analyses for Binary Data

Descriptive statistics for categorical variables (eg, proportions) are the percentage (%) and the numerator (n), the denominator (N) used in the percentage calculation, with 95% CIs.

The exact 95% confidence interval (CI) for binary endpoints will be computed using the F distribution (Clopper-Pearson¹). If r is the number of responses and n is the number of subjects, then it follows that p = r/n is the estimate of the proportion of response. An exact 95% CI can be computed by solving the following 2 equations. For the lower limit p_L ,

$$p_L = \frac{rF_L}{(rF_L + (n-r+1))}$$

and for the upper limit p_U ,

$$p_U = \frac{(r+1)F_U}{(n-r) + (r+1)F_U}$$

where F_L is the quantile from the F distribution for α =0.025, with numerator degrees of freedom equal to 2r and denominator degrees of freedom equal to 2(n-r+1). F_U is the quantile from the F distribution for α =0.975, with numerator degrees of freedom equal to 2(r+1) and denominator degrees of freedom equal to 2(n-r). When r equals 0, F_L should be set equal to 1.0 so p_L equals 0. When r equals n, F_L should be set equal to 1.0 so p_U equals 1.0.

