3.3. Number of Subjects

A total of 565 subjects will be randomized (approximately 188 subjects per arm). Assuming a 15% dropout rate at the time of Dose 3, approximately 160 subjects per arm would be evaluable for immunogenicity. Subjects who withdraw or are withdrawn from the study after randomization will not be replaced, regardless of the reason for withdrawal.

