3.2. Secondary Endpoints

[figure not shown]
- Pneumococcal serotype-specific immunoglobulin G (IgG) concentrations of the c7vPnC serotypes at 1 month after Dose 3.
- Pneumococcal serotype-specific IgG concentrations of the c7vPnC serotypes at 1 month after Dose 4.

IgG Concentration

Concentrations of anticapsular IgG for the c7vPnC pneumococcal serotypes (8, 10A, 11A, 12F, 15B, 22F, and 33F) will be determined in all subjects at specified time points using the Luminex assay. Results will be reported as IgG concentrations.

CCI Antibody

concentrations above the LLOQ are considered accurate and their quantitated values will be reported. Values below the LLOQ, denoted as below the limit of quantification (BLQ), will be set to $0.5 \times \text{LLOQ}$ for analysis.

To support the secondary endpoints, proportions of subjects with serotype-specific IgG concentrations equal to or above the reference concentrations at 1 month after Dose 3 noted below will be calculated.

[figure not shown]
Serotype-specific IgG reference concentrations are defined below.

[figure not shown]
• $\geq 0.35 \mu g/mL$ will be used for serotypes 8, 10A, 11A, 12F, 15B, 22F, and 33F.

Geometric mean concentrations (GMCs) will be calculated and summarized for 1 month after Dose 3 and 1 month after Dose 4.

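### The SAP's Clopper-Pearson rule for r = n resets F_L where F_U is meant; coded as written, a 100% proportion gets a lower limit that is too high

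*SAP*

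**What the plan says.** SAP section 5.2.1 (Analyses for Binary Data) states the method: "The exact 95% confidence interval (CI) for binary endpoints will be computed using the F distribution", with Clopper-Pearson named. It then gives two formulas:

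- Lower limit: p_L = r·F_L / (r·F_L + (n − r + 1)), where F_L is the 0.025 quantile of F with 2r and 2(n − r + 1) degrees of freedom.
- Upper limit: p_U = (r + 1)·F_U / ((n − r) + (r + 1)·F_U), where F_U is the 0.975 quantile of F with 2(r + 1) and 2(n − r) degrees of freedom.

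Two boundary rules follow. For r = 0, F_L is set to 1.0, which gives p_L = 0. For r = n, the text reads "When r equals n, F_L should be set equal to 1.0 so p_U equals 1.0".

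Protocol sections 9.3.1 and 9.4 name the Clopper-Pearson method but give no formulas, so nothing elsewhere in the two documents corrects the second rule.

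**The concern.** The r = n rule prescribes an action that cannot produce its stated result: p_U does not contain F_L. It also leaves the real difficulty untouched. At r = n, F_U has 2(n − r) = 0 denominator degrees of freedom and does not exist, while F_L has 2n and 2 degrees of freedom and is an ordinary quantile. The sentence looks like the r = 0 rule repeated with one symbol left unchanged.

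A programmer who follows it literally replaces a valid F_L by 1.0 and so changes the lower limit. When the estimate is 100%, the lower limit is the only informative end of the interval, and the change always makes the result look more precise than it is.

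The most plausible place for a 100% result is the supporting summary in SAP section 3.2, the "proportions of subjects with serotype-specific IgG concentrations equal to or above the reference concentrations at 1 month after Dose 3". It is tabulated with a Clopper-Pearson interval for seven serotypes by vaccine group (SAP section 6.2.1).

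**Working it through.** **Inputs.** The formulas, degrees of freedom and boundary rules come from SAP section 5.2.1. For illustration, n = 160, because protocol section 3.3 expects that "approximately 160 subjects per arm would be evaluable for immunogenicity" (188 × 0.85 = 159.8). Other values of n are noted where used.

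**Step 1: do the formulas work away from r = n?** They were coded with F quantiles and compared with the beta-quantile form of Clopper-Pearson. At n = 160 the two agree to rounding:

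- r = 1: 0.000158 to 0.034329
- r = 50: 0.241654 to 0.390446
- r = 159: 0.965671 to 0.999842

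**Step 2: the r = 0 rule.** With F_L = 1.0, p_L = 0 / (0 + n + 1) = 0. This is correct, and a substitute is needed because F_L would have zero numerator degrees of freedom.

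**Step 3: upper limit at r = n.** p_U = (n + 1)·F_U / (0 + (n + 1)·F_U), which equals 1 for any finite positive F_U. The plan's figure of 1.0 is therefore correct, but reaching it through the formula requires a value for F_U. Setting F_L supplies none; the software returns a missing value for F_U and hence for p_U.

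**Step 4: lower limit at r = n = 160, correctly computed.** F_L is the 0.025 quantile of F(320, 2) = 0.26797.

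p_L = 160 × 0.26797 / (160 × 0.26797 + 1) = 0.97721.

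Closed-form check: the limit solves p^n = 0.025, so p_L = 0.025^(1/160) = 0.97721. The two agree.

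**Step 5: lower limit at r = n = 160 with the rule as written.** F_L = 1.0, so p_L = 160 / (160 + 1) = 0.99379. The probability of 160 out of 160 at that limit is (160/161)^160 = 0.369, where the exact method requires 0.025.

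**Step 6: comparison with the neighbouring result.** At 159/160 the boundary rule does not apply and the lower limit is 96.57%. One more responder should raise it by 97.72 − 96.57 = 1.15 points. The rule as written raises it by 99.38 − 96.57 = 2.81 points.

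**Step 7: other denominators.**

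| n (all responders) | Rule as written, n/(n+1) | Exact, 0.025^(1/n) | Excess (points) |
|---|---|---|---|
| 50 (assumed) | 98.04% | 92.89% | 5.15 |
| 100 (assumed) | 99.01% | 96.38% | 2.63 |
| 160 (protocol 3.3, evaluable) | 99.38% | 97.72% | 1.66 |
| 188 (protocol 9.1, randomized) | 99.47% | 98.06% | 1.41 |
| 230 (SAP Table 2, per group) | 99.57% | 98.41% | 1.16 |

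**Step 8: how often could r = n occur?** The documents give no response rates for the c7vPnC serotypes, so this is an assumption. For one serotype in one group with n = 160, the chance is p^160: 0.04 at a true rate of 98%, 0.20 at 99%, 0.45 at 99.5% and 0.85 at 99.9%.

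**The case against.** The best reply is that this is a self-correcting slip. The sentence states its intended outcome, the formula above it shows that only F_U can deliver that outcome, and the named method is standard. Any validated exact routine gives the right interval without consulting the text. This stands, and it is why the point is minor.

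A second reply is that formula-only coding of the rule leaves F_U undefined, so the program would show a missing upper limit at the first 100% cell and someone would notice. That is true of such code. But the sentence also dictates that p_U be 1.0. A programmer who hard-codes that value and sets F_L to 1.0, as told, gets a normal-looking interval with a wrong lower end and no warning.

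A third is that the text was machine-read from PDF and the finding rests on one subscript. The L and U subscripts elsewhere in the section, including p_U in the same sentence, read correctly, so a reading error is unlikely. It can be settled by looking at the source file.

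Finally, nothing is decided on these intervals: SAP section 5.1 says that "no formal statistical decision rules apply in this study". That limits the consequence to a displayed figure. It also means that the displayed estimates and intervals are themselves the study's result.

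**Conclusion.** The r = n rule in SAP section 5.2.1 is wrong as written: it names F_L where F_U is needed. The intended upper limit of 1.0 is correct, the r = 0 rule is correct, and every result with r < n is unaffected.

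If the rule is coded literally, the lower limit for a 100% proportion is too high, by 1.66 percentage points at n = 160 and by more at smaller n. The result is then no longer an exact 95% interval. This consequence rests on two conditions that the documents do not settle: that the interval is hand-coded from this sentence, and that some cell reaches 100%. Severity is minor, with no effect on any decision rule.

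**What to change.** In the r = n sentence of SAP section 5.2.1, replace F_L by F_U. Optionally add that F_L keeps its 0.025 quantile with 2n and 2 degrees of freedom, so that p_L = 0.025^(1/n). If a custom macro is used, add one test case: 160/160 should return 97.72% to 100%. The cost is one symbol and one test; no endpoint, data or design element changes.

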5.2.2. Analyses for Continuous Data

Unless otherwise stated, descriptive statistics for continuous variables are n, mean, median, standard deviation, minimum, and maximum.

[figure not shown]
5.2.2.1. Geometric Mean (GM)

Geometric means will be computed along with associated 95% CIs. The GM will be calculated as the mean of the assay results after making the logarithm transformation and then back transformation to its original scale. Two-sided 95% CIs will be obtained by taking log transforms of concentrations, calculating the 95% CI with reference to the t-distribution, then exponentiating the confidence limits.

5.3. Methods to Manage Missing Data

For the analysis of safety endpoints, the sponsor data standard rules for imputation will be

6. ANALYSES AND SUMMARIES

6.1. Primary Endpoints

6.1.1. Local Reactions

6.1.1.1. Primary Analysis

Endpoints: Proportions of subjects reporting prompted local reactions (redness, swelling, and pain at the injection site) within 7 days of each dose

- Analysis time points: Within 7 Days Dose 1; Within 7 Days Dose 2; Within 7 Days - Dose 3; Within 7 Days - Dose 4; Within 7 Days - Supplemental Dose
- Analysis population: Dose 1 to Dose 3 safety population for Doses 1 to 3, Dose 4 safety population for Dose 4, Supplemental dose safety population for supplemental Dose
- Analysis methodology: Descriptive statistics
- Supporting objective: Primary Objective

Reporting results:

Proportions of subjects reporting prompted local reactions will be summarized by maximum severity level. The percentage (%) and the numerator (n) and the denominator (N) used in the percentage calculation, and corresponding 95% Clopper-Pearson CI will be presented for each vaccine group at each time point.

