9.2. Analysis Populations

The safety population will include all Group 1 and Group 2 subjects who receive at least 1 dose of c7vPnC and all Group 3 subjects who receive at least 1 dose of Prevnar 13. Subjects will be assigned to vaccine groups corresponding to the vaccine series actually received. The safety population will be the only analysis population for the primary endpoints.

The Dose 3 evaluable immunogenicity population will include any subject:

1. Who was eligible for the study.

- 2. Who was randomized and met the SAP-specified age window on the first day of vaccination for the randomized group (age windows will be same for Groups 1 and 3, but different for Group 2).
- 3. Who received c7vPnC and/or Prevnar 13, as randomly assigned, through Dose 3.
- 4. Who had an IgG concentration for at least 1 serotype 1 month after Dose 3.
- 5. Whose blood collection was within the SAP-specified window after Dose 3.
- 6. Who had no other major protocol deviations as determined by the clinician or medical monitor.

Additional criteria may be described in the SAP. The Dose 3 evaluable immunogenicity population will be the primary analysis population for immunogenicity results from the blood collected 1 month after Dose 3.

The Dose 4 evaluable immunogenicity population will include any subject:

- 1. Who was eligible for the study.
- 2. Who was randomized and met the SAP-specified age window on first day of vaccination for the randomized group (age windows will be same for Groups 1 and 3, but different for Group 2).
- 3. Who received the assigned vaccine, as randomized, within the defined window for Dose 4 as specified in the SAP.
- 4. Who received the vaccine to which he or she was randomly assigned at all 4 doses.
- 5. Who had an IgG concentration for at least 1 serotype 1 month after Dose 4.
- 6. Whose blood collection was within the SAP-specified window after Dose 4.
- 7. Who had no other major protocol deviations as determined by the clinician or medical monitor.

Additional criteria are described in the SAP. The Dose 4 evaluable immunogenicity population will be the primary analysis population for immunogenicity results after Dose 4.

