9.4. Safety Analysis

All safety analyses will be performed using the safety population.

Descriptive statistics for local reactions for the c7vPnC injection site in Groups 1 and 2 and the Supplemental Dose in Group 3, as well as the Prevnar 13 site in Group 3, and systemic events from Day 1 to Day 7 will be presented by severity and cumulatively across severity levels. Descriptive statistics will include proportions of subjects with the indicated endpoint and the associated Clopper-Pearson 95% CIs. Local reactions will be compiled for each dose for each group (Doses 1, 2, 3, and 4 and the Supplemental Dose) separately and compiled across all 4 doses of the same group.

AEs (including nonserious AEs, SAEs, and NDCMCs) will be compiled over 2 intervals: from Dose 1 to 1 month following Dose 3 and from Dose 4 to 1 month following Dose 4/Supplemental Dose. SAEs and NDCMCs will be summarized from Dose 1 until 6 months after Dose 4/Supplemental Dose. The descriptive statistics for AEs will be summarized as the number and percentage of subjects reporting at least 1 event of each preferred term with the associated Clopper-Pearson 95% CIs, arranged by system organ class.

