6.1.2. Systemic Events

6.1.2.1. Primary Analysis

Endpoints: Proportions of subjects reporting prompted systemic events (fever, decreased appetite, irritability, and drowsiness/increased sleep) within 7 days of each dose

- Analysis time points: Within 7 Days Dose 1; Within 7 Days Dose 2; Within 7 Days Dose 3; Within 7 Days Dose 4; Within 7 Days Supplemental Dose
- Analysis population: Dose 1 to Dose 3 safety population for Doses 1 to 3, Dose 4 safety population for Dose 4, Supplemental dose safety population for supplemental Dose
- Analysis methodology: Descriptive statistics
- Supporting objective: Primary Objective

Reporting results:

The percentage (%) and the numerator (n) and the denominator (N) used in the percentage calculation, and corresponding 95% Clopper-Pearson CI will be presented for each vaccine group at each time points.

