6.1.3. Adverse Events

6.1.3.1. Primary Analysis

Endpoint: Proportions of subjects reporting AEs from Dose 1 to 1 month following Dose 3, from Dose 4 to 1 month following Dose 4, and from Supplemental Dose to 1 month following Supplemental Dose

- Analysis time points: Dose 1 to 1 month after Dose 3, and from Dose 4 to 1 month after Dose 4/Supplemental Dose
- Analysis population: Dose 1 to Dose 3 safety population, Dose 4 safety population, Supplemental dose safety population for supplemental Dose
- Analysis methodology: Descriptive statistics
- Supporting objective: Primary Objective

Reporting results:

The percentage (%), number of subjects and the denominator (N) used in the percentage calculation, and corresponding 95% Clopper-Pearson CI will be presented for each vaccine group.

Figures: None

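### Do the Protocol's single safety population and the SAP's dose-interval populations leave the primary safety denominators unsettled?

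*SAP*

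**What the plan says.** Protocol 9.2 defines the safety population as infants in Groups 1 and 2 with at least one dose of c7vPnC and infants in Group 3 with at least one dose of Prevnar 13. It adds: "The safety population will be the only analysis population for the primary endpoints". Protocol 9.4 says the same more broadly: "All safety analyses will be performed using the safety population".

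SAP 4.1 begins in a similar way: "The safety population will be the analysis population for safety and reactogenicity endpoints". Its overall population carries a condition that the Protocol lacks: "and have safety data reported in the study". The same section then defines three additional safety populations: Dose 1 to Dose 3, Dose 4, and Supplemental Dose. The Dose 4 set, for example, is "Subjects receiving Dose 4 and having safety data between Dose 4 and 1 month after Dose 4 for Groups 1 and 2", with a matching rule for Group 3.

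SAP 6.1 assigns these populations endpoint by endpoint:

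- Local reactions (6.1.1.1): "Analysis population: Dose 1 to Dose 3 safety population for Doses 1 to 3, Dose 4 safety population for Dose 4", and the Supplemental Dose population for that dose.
- Systemic events (6.1.2.1): the same split, starting with "Dose 1 to Dose 3 safety population for Doses 1 to 3".
- Adverse events (6.1.3.1): "Analysis population: Dose 1 to Dose 3 safety population, Dose 4 safety population, Supplemental dose safety population for supplemental Dose".
- SAEs and newly diagnosed chronic conditions (6.1.4.1): the overall safety population.

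Both Protocol 9 and SAP 2 let the SAP modify the Protocol's analyses. Only major changes to the primary endpoints or their analysis must also appear in a protocol amendment.

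**The concern.** Three of the four primary endpoints are assigned populations that the Protocol's sentence, read literally, rules out. Amendment 1 kept that sentence. The SAP cites the December 2017 protocol and still carries 690 infants and 230 per arm, so the two texts were visibly not reconciled.

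The primary objective is descriptive, so the reported percentages and intervals are themselves the result. If adverse events after Dose 4 were divided by everyone who had at least one dose, infants who left before Dose 4 would count as event-free. The percentage would then fall as loss rises, and arms with different retention would differ for that reason alone. Unequal retention is plausible: Group 2 has 11 scheduled contacts, Group 1 has seven and Group 3 has eight. In an open-label study, a denominator left open until the data are visible would be a fair criticism.

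**Working it through.** **Arm size.** Protocol Table 5 uses N = 188. The chance of at least one event is 1 − (1 − p)^188. This gives 0.6103 at p = 0.5%, 0.8488 at 1% and 0.9999 at 5%, matching the printed 0.610, 0.849 and >0.999. Protocol 3.3 also reproduces: 188 × 0.85 = 159.8, about 160.

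**Size of the possible difference.** Let d be the share of the safety population that does not receive Dose 4, and r the number of infants with an adverse event after Dose 4. The Dose 4 population gives r / [188(1 − d)] and the overall population gives r / 188. The second equals the first multiplied by (1 − d).

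Neither the adverse event risk nor the loss before Dose 4 is in the documents. The 15% in Protocol 3.3 is an immunogenicity assumption at Dose 3. The table therefore assumes a risk of about 20% and varies d. The figure of 188 is a ceiling for the safety population, since not every randomised infant need receive Dose 1. Intervals are Clopper-Pearson 95%.

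| Loss d | Dose 4 population | Overall population | Gap (points) |
|---|---|---|---|
| 5% | 36/179 = 20.1% (14.5 to 26.7) | 36/188 = 19.1% (13.8 to 25.5) | 1.0 |
| 15% | 32/160 = 20.0% (14.1 to 27.0) | 32/188 = 17.0% (11.9 to 23.2) | 3.0 |
| 25% | 28/141 = 19.9% (13.6 to 27.4) | 28/188 = 14.9% (10.1 to 20.8) | 5.0 |

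At an assumed risk of 30% and 15% loss, the figures are 48/160 = 30.0% and 48/188 = 25.5%. With equal 20% risk but 10% loss in one arm and 25% in another, the overall population shows 20% × 0.90 = 18.0% and 20% × 0.75 = 15.0%; the Dose 4 populations show 20% in both. With no loss there is no difference.

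**Does the plan lead to the right-hand column?** Two conditions must both hold.

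1. *The Protocol sentence must override SAP 6.1.3.1.* Both documents allow the SAP to modify the Protocol. Within the SAP, the general sentence in 4.1 is followed by the definitions of the three further populations, and 6.1 names one for each endpoint and interval. A programmer who has a general statement and a specific assignment follows the specific one.
2. *Membership of the safety population must mean inclusion in N for every interval.* The Protocol does not say so. Its own endpoint (2.1.2 and 9.4) runs from Dose 4 to one month after Dose 4 or the Supplemental Dose, and an infant who never received Dose 4 has no such interval. SAP 5.2.1 and 6.1.3.1 report the denominator used for each percentage, which leaves room for N to be smaller than the population.

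**Other intervals and endpoints.** The Dose 1 to Dose 3 population requires Dose 1 and some safety data afterwards, so it is nearly the overall population. Adverse events in that interval barely depend on the choice. For prompted events, SAP 5.2 ties each time point to data within 7 days of the dose, so N is probably dose-based under either wording. SAEs and chronic conditions use the overall population in both documents.

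**The added safety-data condition.** Infants are observed for 30 minutes after each of these doses (Protocol 3, SAP 2.2), so almost every vaccinated infant should have some safety data. No material effect on N is shown.

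**The case for a change.** The strongest case for acting is that the Protocol's word is *only*, that it survived Amendment 1, and that Protocol 9 promises an amendment for major changes to a primary analysis. SAP 5.2 anchors the prompted events to each dose but does not mention adverse events, so for those the named population is the main visible guide to N. A few sentences would remove the conflict.

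The literal mismatch stands: a reader who checks the report against Protocol 9.2 will notice it. The rest is weaker. Splitting the safety population by dose received, for endpoints already defined by dose, is closer to implementation than to a major change. The choice is not left until after the data are seen, because SAP 6.1 makes it. Some adverse event derivation rules may also lie in redacted text: SAP 3.1 says the SAE endpoint is computed in a similar way to adverse events, after a blacked-out block. A missing rule on N cannot be inferred from the public version.

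The proposed edits mostly bring the Protocol and SAP 4.1 into line with populations that are already the sensible ones. The alternative, imposing a single population on SAP 6.1, would risk creating the dilution that the concern fears. The old 690 and 230 figures enter no visible analysis.

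**Conclusion.** The concern does not call for a change. Protocol 9.2 and 9.4 and the general sentence in SAP 4.1 are worded more broadly than SAP 6.1. The endpoint-specific assignments in SAP 6.1 settle the tables, and for adverse events after Dose 4 and after the Supplemental Dose they restrict the population to infants who received that dose. Under the plan as it would be carried out, the retention effect is therefore absent.

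The gap of 1 to 5 points at a 20% risk (5% to 25% loss) describes a reading that the Protocol does not state, and it rests on assumed risk and loss. Even then the intervals overlap heavily, and SAP 5.1 sets no test or decision rule that could turn on it. Aligning the wording and the outdated protocol citation at a later revision would be good housekeeping, but no result or conclusion depends on it. This judgement assumes that the redacted parts of the SAP do not contradict SAP 6.1.3.1.
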